#### Basic Information

Category Engineering Change Order

Change Number ECO-002742

Title Pill Swallow Study Document Updates

Description - CP-0003: Protocol updated to version B to change the pill contents from microcrystalline cellulose to potato starch and include a new exclusion criteria for allergies to mock-RaniPill components.  
- Summary of changes for the protocol added  
- Updated all CRFs to replace "subject" with "participant" and add a version date.

#### Additional CRF Edits:

- Screening CRF: Added new exclusion criteria for allergies to mock-RaniPill components.
- Moved Pill Swallow Assessment up the form.
- Post-Swallow Questionnaire: changed VAS score from 0-10 to 0-4.
- SAE Form: added "Final Outcome" field.

Associated Files 10 Reference File(s) + 0 Implementation File(s)

Routings None specified

Approval Deadline None specified

Effectivity 2021/04/28

Expiration Date N/A (This is a permanent Change.)

Lifecycle Status... Completed

...As Of 2021/04/28 03:38:17 PM

Creator [name]

Created On 2021/04/23 06:53:40 AM

Submitter [name]

Submitted On 2021/04/23 11:30:50 AM

**Reason and Justification**

---

Company/Project	Rani
Reason and Justification for Change	Protocol updated to version B to change the pill contents from microcrystalline cellulose to potato starch and add a new exclusion criteria. CRFs updated while creating the database and accommodating protocol changes.

**Impact Assessment**

---

Are other documents affected by this change?	No
Other affected documents	N/A
Design V&V Testing required?	No - Provide justification below.
Design V&V Testing additional info/justification	N/A
Process Validation required?	No - Provide justification below.
Process Validation additional info/justification	N/A
Risk Analysis update required?	No - Provide justification below.
Risk Analysis additional info/justification	N/A
Regulatory Action required?	No - Provide justification below.
Regulatory Action additional info/justification	N/A
Supplier/Partner notification required?	No
Supplier/Partner notification additional info	N/A
Training or re-training required?	No

**ABBREVIATIONS**

Abbreviation	Definition
AE	Adverse Event
CFR	Code of Federal Regulations
CIP	Clinical Investigation Plan
CRF	Case Report Form
CTA	Clinical Trial Agreement
CTM	Clinical Trial Material
CV	Curriculum Vitae
eCRFs	Electronic Case Report Forms
EDC	Electronic Data Capture
EMA	European Medicines Agency
FDA	Food and Drug Administration
GCP	Good Clinical Practice
GET	Gastric Emptying Time
GI	Gastrointestinal Tract
IB	Investigator's Brochure
ICF	Informed Consent Form
ICH	International Conference of Harmonization
ICMJE	International Committee of Medical Journal Editors
IDT	Intestinal Deployment Time
IRB	Institutional Review Board
NSR	Non-Significant Risk
PI	Principal Investigator
SAE	Serious Adverse Event
US	United States

## PROTOCOL SYNOPSIS

Title	Pill Swallow Study
Purpose	A Prospective Study Assessing Participant Experience with Swallowing a Mock Version of the RaniPill™ Capsule ("Mock-RP")
Phase of Clinical Trial	Non-significant risk
Test Device	Mock-RP: Standard 000 capsule shell filled with potato starch weighing similar as the RaniPill™ Capsule, enteric-coated with colorant and lubricous coating
Indication for Use	N/A
Study Objective	Assess a participant's ability to swallow a Mock-RP.
Sample Size	Up to 200 participants will be enrolled with up to 150 participants attempting to swallow the Mock-RP: 30 to 50 participants in each age group. Participation inclusion in an age group stops at 50 participants.
Follow-up	Assessment of the Mock-RP will occur the same day as swallowing the pill. No additional follow-up is anticipated.
General Study Design	A prospective, single-center, open-label, single-arm, observational study enrolling up to 200 men and women volunteers age $\geq 21$ currently using injection therapy to treat chronic disorders (e.g., diabetes (I or II), rheumatoid arthritis, ulcerative colitis, Crohn's disease, ankylosing spondylolisthesis, psoriasis, growth hormone deficiency, hemophilia A) recruited from the general population with up to 150 participants attempting to swallow the Mock-RP after passing protocol required screening. A total of 30 to 50 participants will be included in each of the following age ranges: 21-50, 51-65, 66-75. Participants must meet all inclusion and none of the exclusion criteria prior to attempting to swallow the Mock-RP. Participants will complete a questionnaire on their thoughts on an alternative therapy in pill form. Upon completion of the questionnaire, participants will be requested to swallow a Mock-RP. The Mock-RP will be a standard 000 capsule filled with potato starch weighing similar to the RaniPill™ Capsule. The capsule is protected by an enteric coating with colorant and lubricious coating allowing intact passage through the stomach into the jejunum, where the pH starts dissolving the coating; completely dissolving in the small intestine. After swallowing the Mock-RP, the participant will complete the questionnaire assessing swallowability of the Mock-RP. If the participant was unable to swallow the Mock-RP, they will be asked to attempt to swallow a Calcium dietary supplement (Rapid Release Calcium in Liquid Softgel). Anticipated participant duration is approximately 1 hour.
Inclusion Criteria	Individuals eligible to participate in this study must meet all the following criteria: 

1. Participant age is 21 – 75 years

2. Participant understands the nature of the study, is willing to comply with protocol defined evaluations, and provide written informed consent

3. Participant currently taking injections to treat a chronic disorder

4. Non-pregnant, non-lactating female

 NOTE: Females who are of childbearing potential must have had a negative pregnancy test on day of screening

Exclusion Criteria	
Individuals eligible to participate in this study must not meet any of the following criteria:
 
 
1. Active case of COVID-19.
 
2. History of Dysphagia.
 
3. History of dementia (e.g., Alzheimer's, vascular dementia, dementia with Lewy bodies, etc.).
 
4. Participant self-reports issues with swallowing pills.
 
5. History of drug or alcohol abuse or any other factor that, in the Investigator's opinion, may interfere with the participant's ability to cooperate and comply with the study procedures.
 
6. History of allergic reaction to a component of the Mock-RP
 
7. History which, in the investigator's judgement, makes the participant ineligible or exposes the participant to unacceptable risks
 

Study Endpoints	
 
- Percent of participants successfully swallowing the Mock-RP as reported on the questionnaire.
 
- Assess if participant would choose a pill instead of their current injection therapy if a pill becomes available.
 
- Participant experience with swallowing Mock-RP stratified by number of years using injections.
 
- Participant experience with swallowing Mock-RP stratified by age (21-50, 51-65, 66-75 years).
 
- Participant experience with swallowing Mock-RP stratified by frequency of injection treatment.
 
- All adverse events categorized by type and frequency.
 

Clinical Trial Material (CTM)	Mock-RP
Sponsor:	Rani Therapeutics [name]

## 1 INTRODUCTION

### 1.1 Study Purpose

Rani Therapeutics is sponsoring the Pill Swallow Study, a prospective, single-center, open-label, single-arm, observational study assessing participant experience with swallowing the Mock-RP.

### 1.2 Study Scope

This study will be conducted at one site in the U.S. Up to 200 participants will be enrolled (consented) and up to 150 will attempt to swallow the Mock-RP after passing protocol required screening. Study duration is expected to be approximately three months.

### 1.3 Governing Regulations

The Mock-RP is investigational and classified as a non-significant risk device in the U.S. This Clinical Investigation Plan (CIP) will not be submitted to the FDA for approval. The study will be conducted per 21 CFR Parts 11 (Electronic Records; Electronic Signatures), 50 (Protection of Human Subjects), and 56 (Institutional Review Boards) and conducted in accordance with the relevant parts of the ICH Guidelines for Good Clinical Practice, ethical principles that have their origins in the Declaration of Helsinki and the individual country laws and regulations, whichever afford greater protection to participants. Participating sites will obtain IRB approval prior to beginning study.

## 2 BACKGROUND AND JUSTIFICATION

The RaniPill™ Capsule is an ingestible robotic pill, based on 000 (31 mm by 11 mm) size capsule designed to deliver biopharmaceuticals into the small intestinal wall. The goal of the RaniPill™ Capsule is orally deliver biologics which are currently given via subcutaneous, intramuscular or intravenous injections. The current study will evaluate the ease of swallowing of a pill similar in size to RaniPill™ Capsule.

### 2.1 Mechanism of Action

The RaniPill™ Capsule needs to be swallowed whole to keep its internal delivery mechanism intact. The RaniPill™ Capsule remains intact in the stomach, protected by the enteric coating. As it leaves the stomach and advances along the small intestine by peristalsis, the enteric coating starts to dissolve with the rise in pH. Dissolution of the enteric coating and capsule shell exposes the reaction valve to the intestinal fluid, causing its dissolution and enabling the mixing of citric acid and potassium bicarbonate. The production of carbon dioxide inflates and stabilizes the balloon and aligns the micro syringe perpendicularly to the intestinal wall and, as the piston is released, drives the dissolvable needle into the wall. The microneedle dissolves within minutes and delivers its payload, while the balloon deflates, releases the carbon dioxide, and is excreted through the gastrointestinal tract (GI).

## 2.2 Summary of Prior Clinical Use/History

### 2.2.1 Non-Significant Risk Study

In a non-significant risk (NSR) study, a modified, needleless, medication-free version of the RaniPill™ Capsule was tested in 10 fasting and 10 postprandial healthy volunteers to examine the tolerability of the RaniPill™ Capsule ingestion, gastrointestinal progression, deployment and ultimate excretion of the device remnants, monitored with serial abdominal fluoroscopies. A single RaniPill™ Capsule was orally administered to each subject and radiographically tracked during its transit from the stomach to the small intestine. No adverse events were reported by the subjects in the study.

### 2.2.2 First-In-Human Study

This study was the first demonstration in humans (N=62) of the oral delivery of an injectable biotherapeutic via the orally ingestible RaniPill™ Capsule. This study suggested RaniPill™ Capsule may safely and effectively deliver a wide variety of biotherapeutics currently administered only via parenteral routes. Biotherapeutic was successfully delivered with a bioavailability of 65%. All devices were confirmed to have successfully been excreted by all subjects without sequelae. No serious or unexpected adverse events were observed during the transit of the RaniPill™ Capsule through the gastrointestinal tract.

## 2.3 Justification

In the previous studies, none of the participants reported any issues with swallowing the RaniPill™ Capsule. These studies were conducted in young healthy volunteers. The goal of the present study is to enroll patients of different age groups who are taking injections and will be potential candidates for the RaniPill™ Capsule when it becomes available. Understanding patient treatment preference is important in early drug development. Collecting data on patient preference of new and current therapies may help inform the benefit-risk assessment of the product (**Bouvy 2020**). The ease of swallowing oral drug therapy is a key determinant for patient acceptability. The European Medicines Agency (EMA) in 2017 released a reflection paper regarding pharmaceutical development of medicines for use in older populations and suggested swallowability and palatability are key characteristics for patient acceptability (**EMA 2017**). Ternik, et al., conducted a workshop dedicated to acceptability assessments for pediatric pharmaceutical products with similar conclusion of swallowability and palatability contributing to oral drug acceptability in pediatric patients (**Ternik 2018**). Swallowability and palatability ratings of new oral drug therapies may drive patient selection to new oral therapies vs their current injection options.

The study will test the swallowability of a pill similar in shape and size to the RaniPill™ Capsule to be referred to as Mock-RP.

## 3 INTENDED USE, INDICATIONS FOR USE AND PRODUCT DESCRIPTION

### 3.1 Intended Use

The Mock-RP is not intended to deliver a treatment for a disease.

### 3.2 Proposed Indication for Use

The Mock-RP will not be used to treat disease in participants.

### 3.3 Investigational Clinical Trial Material (CTM) Description

In this study, a Mock-RP capsule shell, similar to weight, shape and size of the RaniPill™ Capsule, will be filled with potato starch, enteric-coated with colorant and lubricous coating (**Figure 1**).

Figure 1: Enteric-coated Capsule

The potato starch is considered natural and produced directly from a peeled, ground, washed and dried potato. The Mock-RP is an investigational CTM and will be manufactured by Rani Therapeutics. The Mock-RP will not contain a needle or drug and will be packaged and labeled individually in a plastic vial with a snap on cap. The Mock-RP will be delivered directly to the investigator by the sponsor's representative and stored at room temperature under standard security protocols.

## 4 METHODOLOGY AND ENDPOINTS

The objective of this study is to assess a participant's ability to swallow a Mock-RP.

Eligible participants will complete a questionnaire to assess their experience on an alternative therapy in pill form. Upon completion of the questionnaire, participants will be requested to swallow a Mock-RP then complete a questionnaire assessing a participant's ability to swallow the Mock-RP. Anticipated participant duration is approximately 1 hour.

### 4.1 Study Endpoints

Several endpoints will be evaluated, including:

- Percent of participants successfully swallowing the Mock-RP as reported on the questionnaire.
- Assess if participant would choose a pill instead of their current injection therapy if a pill becomes available.
- Participant experience with swallowing Mock-RP stratified by number of years using injections.
- Participant experience with swallowing Mock-RP stratified by age (21-50, 51-65, 66-75 years).
- Participant experience with swallowing Mock-RP stratified by frequency of injection treatment.
- All adverse events categorized by type and frequency.

	PILL SWALLOW STUDY PROTOCOL	Doc No.:	CP-0003
		Revision:	C
		Page:	Page 11 of 12

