## 5 STUDY SAMPLE SIZE

As a prospective, single-center, open-label, single-arm, observational study, no statistical criteria for sample size are required. A total of 30 to 50 participants in each age group (21-50, 51-65, 66-75), for a total of up to 150 participants will provide sufficient data to characterize the endpoints, as well to evaluate swallowing trends between subgroups.

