## 7.3 Enrollment

Up to 200 men and women volunteers age  $\geq 21$  currently using injection therapy will be recruited from the general population and enrolled (consented) and up to 150 participants will attempt to swallow the Mock-RP after passing protocol required screening. A total of 30 to 50 participants will be included in each of the following age (years) groups: 21-50, 51-65, 66-75. Participants must meet all inclusion and none of the exclusion criteria prior to swallowing the Mock-RP.

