### **13.1 Analysis Cohorts**

All participants who attempt to swallow the Mock-RP in the study are included in the Analysis Cohort used for evaluating swallowability of the Mock-RP.

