### **13.2 Sample Size Justification**

As an observational study, no hypothesis tests are planned. All data will be summarized. Nevertheless, with the sample size proposed for the study, the following levels of precision of the estimates, expressed as the width of the confidence interval, can be achieved:

1. The width of the exact 95% two-sided confidence interval for percentages will be no wider than +/- 14.5% with 50 participants contributing to the estimate of the proportion and will be no wider than +/- 8.3% with 150 participants.
2. The width of the 95% two-sided confidence interval for the mean will be equal to +/- 27.7% of the standard deviation with 50 participants contributing to the estimate of the mean and will be equal to +/- 16.0% of the standard deviation with 200 participants.

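### Results by years on injections and by injection frequency are planned without age, so a duration trend cannot be told apart from an age trend

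*Combined protocol and SAP*

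**What the plan says.** Recruitment is by age quota. Section 7.3 states: "A total of 30 to 50 participants will be included in each of the following age (years) groups: 21-50, 51-65, 66-75". The synopsis adds: "Participation inclusion in an age group stops at 50 participants". No other participant characteristic has a quota.

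The first endpoint in section 4.1 is "Percent of participants successfully swallowing the Mock-RP as reported on the questionnaire". Section 13.1 fixes the denominator: "All participants who attempt to swallow the Mock-RP in the study are included in the Analysis Cohort". No weights for the age bands are given.

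Two further endpoints concern injection history: "Participant experience with swallowing Mock-RP stratified by number of years using injections" and "Participant experience with swallowing Mock-RP stratified by frequency of injection treatment". Experience by age band is a separate item in the same list. The protocol text gives no cut-points for years or frequency, and it neither crosses these factors with age nor adjusts for it.

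Section 13 provides frequency tables, summary statistics, exact intervals for proportions and asymptotic intervals for means. Section 13.2 plans no hypothesis testing and gives precision for a percentage both at 50 participants and at 150 (for the latter, "will be no wider than +/- 8.3% with 150 participants"). Section 5 says the sample is enough to look at how swallowing varies between subgroups.

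**The concern.** The protocol samples by age because its earlier studies were in young volunteers and it now wants results across the adult age range (section 2.3). Age is thus treated as something that may affect swallowing. Years on injections is tied to age: a person of 30 cannot have injected for 40 years, while a person of 70 can. If older participants find the capsule harder, and long-duration users are older on average, the one-way table by years on injections will show a worse result for long-duration users even when duration has no influence.

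At stake is the reading of that table, and to a lesser degree the injection-frequency table. Section 5 offers the data for subgroup trends, and a reader will compare the rows. As planned, the comparison cannot say whether it reflects years of injecting or age.

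A smaller issue affects the success percentage. Pooled over attempters, it weights each band by the number recruited into it, and the endpoint list does not say explicitly that success is also reported by band.

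**Working it through.** **The plan's own precision figures.** The largest half-width of the exact (Clopper-Pearson) 95% interval, over all possible counts, is 14.47% at n = 50 and 8.26% at n = 150. Both match section 13.2 (14.5% and 8.3%).

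**Inputs for the duration check.**
- Band sizes: 50/50/50, the cap in the synopsis; other fills between 30 and 50 are tried below.
- Success by band, young to old: 98/95/85%. This is an assumption, since the documents give no age-specific rates.
- Long-duration users as a share of each band: 20/45/65%. Also an assumption.
- Duration has no effect within a band.

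**Crude result at 50/50/50.**
- Long-duration users: 10, 22.5 and 32.5, total 65. Success = (10 × 0.98 + 22.5 × 0.95 + 32.5 × 0.85)/65 = 58.8/65 = 90.5%.
- Short-duration users: 40, 27.5 and 17.5, total 85. Success = (40 × 0.98 + 27.5 × 0.95 + 17.5 × 0.85)/85 = 80.2/85 = 94.4%.
- Spurious gap: 3.9 points. Standardised to the same band weights, the gap is zero, because the rates within each band are equal.

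**How it moves with the assumptions (50/50/50).**
- Long-duration shares of 30/40/50%: 1.8 points. Shares of 10/40/70%: 5.4 points.
- Milder gradient of 98/96/92% with shares 20/45/65%: long 61.3/65 = 94.3%, short 81.7/85 = 96.1%, gap 1.8 points.
- Steeper gradients with shares 30/50/70%: 4.0 points for 95/90/80% and 8.0 points for 95/85/65%.
- No age gradient, or equal long-duration shares in every band: zero.

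**Does quota fill drive it?** With 98/95/85% and 20/45/65%, over every permitted fill:
- Smallest gap, at 30/50/30: long 43.83/48 = 91.3%, short 58.57/62 = 94.5%, gap 3.2 points.
- Largest gap, at 50/30/50: long 50.25/56 = 89.7%, short 69.75/74 = 94.3%, gap 4.5 points.

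The gap is present at every fill, including a balanced one.

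**Sampling error of the contrast at 50/50/50.** Crude SE = √(0.905 × 0.095/65 + 0.944 × 0.056/85) ≈ 4.4 points, so the 95% margin is about ±8.7 points.

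**Pooled success percentage (98/95/85%).**
- Fill 50/50/30: (49 + 47.5 + 25.5)/130 = 93.8%.
- Fill 30/30/50: (29.4 + 28.5 + 42.5)/110 = 91.3%.
- Equal weights: (98 + 95 + 85)/3 = 92.7% at any fill.

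These two fills are the extremes, so the pooled figure is at most 1.4 points from the equal-weight value. The exact 95% half-widths are about 4.5 points (122/130) and 5.8 points (100/110).

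**The case against.** The strongest reply is that this is a descriptive study. It tests nothing, and the protocol nowhere says that the duration table is meant to isolate an effect of duration. A crude table correctly describes the people in it. The rates and shares above are assumed, the exclusions for dysphagia and self-reported pill problems may flatten any age gradient, and a 4-point gap lies inside the ±8.7-point margin. The endpoint is experience, whereas the illustration uses success. All of this stands as a limit on the size of the point. It does not remove it: confounding does not shrink as numbers grow, the interval does not reflect it, and it acts on a mean rating as it does on a percentage. For injection frequency, the documents give no reason to expect a particular link with age, so the case there is weaker.

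Three stronger readings are tempting, and the documents do not support them.
- A reader might infer that the pooled percentage has no fixed meaning. It has a plain one, the proportion of attempters who succeeded. It depends on quota fill only if success varies with age, and by little under the gradient assumed here.
- A reader might infer that the injection-history results follow quota fill instead of swallowing ability. The check shows otherwise: the problem is age confounding, with a similar gap at every fill.
- A reader might infer that section 13.2 gives precision only for the pool of 150. It also gives it at 50, the cap for one band. With the stratified-by-age endpoint and exact intervals for proportions, success by band is reasonably read as intended, though not stated.

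**Conclusion.** The point holds for the injection-history breakdowns. As planned, an apparent trend by years on injections cannot be separated from an age trend, whatever the quota fill. Under the main assumptions the spurious gap is about 4 points; it is 1.8 to 5.4 points over the other long-duration shares tried, larger with steeper age gradients, and zero if success does not vary with age or if duration is unrelated to it. These figures are illustrations, because the documents contain neither age-specific success nor duration by age. The point is weaker for injection frequency.

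For the success percentage, only a clarification is needed: its shift from an equal-weight value is at most about 1.4 points under the assumed gradient, well inside its interval. This is a worthwhile improvement to a descriptive plan and does not threaten the study's main result.

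**What to change.** In sections 4.1 and 13:

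1. State that results by years on injections will be shown adjusted for age band beside the crude table. Use either one model of the experience rating with age band included, or direct standardisation to stated band weights. Do the same for injection frequency. Fix the categories of both factors in advance.
2. State that percent swallowing will be reported for each age band with its exact interval, and label the pooled percentage as reflecting the quota mix. Replacing it with an equal-weight headline is optional; equal weights represent no stated population either.

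No new data are needed, since the quotas already require age band to be recorded. The cost is precision where an age-by-duration cell is sparse: a 20% long-duration share of a band of 30 is 6 people, and more duration categories would make cells thinner. With two categories at 50/50/50 the cost is negligible. Under the main assumptions the equal-weight standardised contrast has SE = √{[0.0196 × (1/10 + 1/40) + 0.0475 × (1/22.5 + 1/27.5) + 0.1275 × (1/32.5 + 1/17.5)]/9} ≈ 4.4 points, about the same as the crude contrast. If an equal-weight overall percentage were also adopted, its SE at 50/50/30 would be about 2.5 points against 2.1 for the crude pool.

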### 7.7 Visit Procedures

#### 7.7.1 Pre-Swallow Questionnaire

Participant will complete the pre-swallow questionnaire to self-report any historical issues with swallowing pills, current medicines they take in pill form, and if they would take an alternative therapy in pill form.

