## 13 STATISTICAL METHODS

Categorical data will be summarized using frequency tables, presenting the participant counts and relative percentages. Continuous variables will be summarized by the mean, standard deviation, median, minimum and maximum. The SAS system or equivalent statistical package will be used to perform all analyses. Exact confidence intervals will be generated for estimates of proportions. Asymptotic confidence intervals will be generated for estimates of means. Except where otherwise noted, p-values of all tests will be reported without any correction for the multiplicity of tests performed.

	PILL SWALLOW STUDY PROTOCOL	Doc No.:	CP-0003
		Revision:	C
		Page:	Page 26 of 27

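### Do the missing bands for years on injections and injection frequency, with a stray p-value sentence, require a change to the plan?

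*Combined protocol and SAP*

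**What the plan says.** Section 4.1 and the synopsis list three stratified endpoints. Age has bands (21-50, 51-65 and 66-75 years). The other two, "Participant experience with swallowing Mock-RP stratified by number of years using injections" and "Participant experience with swallowing Mock-RP stratified by frequency of injection treatment", have none. Section 13 gives no rule for forming or merging strata and none for a participant on more than one injection.

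Section 5 says that 30 to 50 participants per age group, up to 150 in all, will be enough to describe the endpoints, "as well to evaluate swallowing trends between subgroups".

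Section 13 specifies frequency tables, exact confidence intervals for proportions and asymptotic intervals for means. It adds: "Except where otherwise noted, p-values of all tests will be reported without any correction for the multiplicity of tests performed". Section 13.2 then states: "As an observational study, no hypothesis tests are planned". Its precision for proportions is given for 50 and 150 participants only.

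**The concern.** One stratifier is banded and two are not, so the two tables cannot be produced without a choice that the protocol does not record. The study is open-label, so that choice could be made with the results in view. A cut picked because it shows the widest gap will overstate the relation even when there is none and no test is run. Section 5 promises a look at trends between subgroups, and Section 18 promises publication, so a reader could be misled.

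Two further points seem to add weight. Only the age groups have controlled sizes, so strata on the other two variables could be small and imprecise. And the p-value sentence could let a split chosen late carry a nominal p-value with no label.

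**Working it through.** **1. The plan's own precision.** Take the Clopper-Pearson 95% interval for x successes in n, and find the largest half-width over all x. This gives 14.47 points at n = 50 and 8.26 at n = 150, matching the 14.5 and 8.3 in Section 13.2. On the same basis n = 30, the floor for an age group, gives 18.7 points.

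**2. Small strata.** Suppose a stratum holds 10% of participants (an assumption). With 90 participants (3 × 30) that is n = 9, and with 150 it is n = 15. The worst-case half-widths are 32.5 and 26.1 points, but they arise near 50% success. At success rates near 90% they are smaller: 8/9 gives 51.8% to 99.7%, half-width 24.0, and 14/15 gives 68.1% to 99.8%, half-width 15.9. Section 13.2 is conditional on 50 or 150 participants contributing and promises nothing for other sizes.

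**3. Effect of choosing the split.** Assumptions: one yes/no item, no true relation with years on injections, 20,000 simulated studies per setting, and the same participants re-cut at each split. The five candidate cuts are at the 20th, 35th, 50th, 65th and 80th percentiles. Entries are median gaps in percentage points; for bands, the gap is highest minus lowest.

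| Rule | 90% success, n = 90 / 150 | 95% success, n = 90 / 150 |
|---|---|---|
| One pre-set median split | 4.4 / 2.7 | 2.2 / 2.7 |
| Largest of five splits | 9.7 / 7.5 | 6.9 / 5.3 |
| Three pre-set equal bands | 10.0 / 6.0 | 6.7 / 4.0 |
| Five pre-set bands (10/20/20/30/20%) | 16.7 / 13.3 | 11.1 / 10.0 |

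The first two rows alone suggest that choosing late multiplies the gap by 9.7 / 4.4 = 2.2 or 7.5 / 2.7 = 2.8 at 90% success. The third row shows that three bands fixed in advance, as age has, give gaps of about the same size by chance alone. Searching every cut from the 10th to the 90th percentile gives 13.8 / 11.1 at 90% success, which five pre-set bands exceed. Nothing in the documents suggests such a search.

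**4. If p-values were reported.** With n = 150 and no true relation, the chance of at least one nominal p < 0.05 is about 5% for one pre-set split, 12-14% for the best of three cuts, 19% for the best of five and 25% for the best of nine. These rates matter only if tests are run. Section 13 names none and 13.2 plans none.

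**5. Does the outcome match?** The stratified endpoints concern the swallowing experience. Section 7.7.3 records this as palatability and swallowability, and the change order mentions a 0-4 visual analogue score. The percentage who swallow successfully is a separate endpoint with no stratification. The yes/no simulation is therefore only a stand-in.

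**The case for a change.** The strongest case for a change is that the omission lies inside the protocol's own endpoint list and costs a few sentences to repair. Sections 7.6.2, 7.6.3 and 7.7.1, which describe what is recorded, name neither the duration nor the frequency of injections, and the protocol does not point to the case report forms for strata. Even if those forms fix categories, categories can be merged after the data are seen. Section 4.2 names evaluation of the data as a possible source of bias and offers nothing on this. The comparison with three pre-set bands is also not like for like: a highest-to-lowest range over three groups naturally exceeds a gap between two, and a fixed range is not selected.

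Much of this stands as description. The bands are absent, and Sections 13 and 13.2 sit awkwardly together. The point about ranges is fair, and the false-positive rates in step 4 are the cleaner measure of selection, but they need tests that the plan does not call for. What does not stand is the inference that the tables are unsound. Section 14.1 says that all required data go into standardized electronic forms, and the change order shows the forms under change control, so the categories may already be set. Silence in a summary of the questionnaires does not show that the variables go uncollected.

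**Conclusion.** No change is needed. The protocol leaves out bands for two descriptive endpoints, and no rule that it does state gives a wrong result. An analyst of a one-visit, single-arm study would use the form's categories or ordinary bands, show the number in each, and attach the exact interval that Section 13 already requires for proportions. Small strata would then show their own uncertainty. The overall swallowing percentage and the safety summary are unaffected.

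On size, the best of five splits gives a typical chance gap of 9.7 or 7.5 points at 90% success (n = 90 or 150), against 10.0 or 6.0 for three fixed bands, so fixing bands would not remove gaps of that order. The half-widths of 32.5 and 26.1 points are worst cases for an assumed 10% stratum and are no failure of 13.2.

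The p-value sentence is a wording slip. It says how p-values would be reported but orders no test, and removing it would change no result.

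This rests on the study staying descriptive, as 13.2 states, and on the assumed success rates of 90-95%. It does not depend on what the unseen forms contain. If they leave the bands open, the choice is still a modest one, shown with its counts and intervals.
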